#### **11.1.2. Method, Frequency, and Time Period for Detecting Adverse Events and Reporting Serious Adverse Events**

Reports of AEs are to be collected from the time the subject signs the informed consent through the follow-up period ending on Day 14. The Investigator or designee must completely and promptly record each AE. The Investigator should attempt, if possible, to establish a diagnosis based on the presenting signs and symptoms. In such cases, the diagnosis should be documented as the AE and not the individual sign/symptom. If a clear diagnosis cannot be established, each sign and symptom must be recorded individually. If a final diagnosis is established during evaluation or treatment, the source documents will be updated accordingly.

The Investigator should attempt to follow all unresolved AEs and/or SAEs observed during the study until they are resolved, or are judged medically stable, or are otherwise medically explained.

#### **11.1.3. Definition of Severity**

All AEs will be assessed (graded) for severity and classified using the DAIDS criteria for grading AEs (see [Section 16.2](#)). Any adverse events not covered by the DAIDS criteria will be assessed and classified into one of 4 clearly defined categories as follows:

- |                         |   |
|-------------------------|---|
| Mild:            | (Grade 1): Transient or mild symptoms; no limitation in activity; no intervention required. The AE does not interfere with the participant's normal functioning level. It may be an annoyance.  |
| Moderate:        | (Grade 2): Symptom results in mild to moderate limitation in activity; no or minimal intervention required. The AE produces some impairment of functioning, but it is not hazardous to health. It is uncomfortable or an embarrassment. |
| Severe:          | (Grade 3): Symptom results in significant limitation in activity; medical intervention may be required. The AE produces significant impairment of functioning or incapacitation.  |
| Life threatening | (Grade 4): Symptoms causing inability to perform basic self-care functions OR Medical or operative intervention indicated to prevent permanent impairment, persistent disability, or death  |

#### 11.1.4. Definition of Relationship to Study Drug

The Principal Investigator or medically qualified designee must review each AE and make the determination of relationship to study drug using the following guidelines:

- Not Related:** The event can be readily explained by other factors such as the subject's underlying medical condition, concomitant therapy, or accident, and no temporal relationship exists between the study drug and the event.
- Unlikely:** The event does not follow a reasonable temporal sequence from drug administration and is readily explained by the subject's clinical state or by other modes of therapy administered to the subject.
- Possibly Related:** There is some temporal relationship between the event and the administration of the study drug and the event is unlikely to be explained by the subject's medical condition, other therapies, or accident.
- Probably Related:** The event follows a reasonable temporal sequence from drug administration, abates upon discontinuation of the drug, and cannot be reasonably explained by the known characteristics of the subject's clinical state.
- Definitely Related:** The event follows a reasonable temporal sequence from administration of the medication, follows a known or suspected response pattern to the medication, is confirmed by improvement upon stopping the medication (dechallenge), and reappears upon repeated exposure (rechallenge, if rechallenge is medically appropriate).

#### 11.1.5. Reporting Serious Adverse Events

Any SAE must be reported by phone or email to the Sponsor medical monitor and in writing via email or fax using the SAE report form within 24 hours of the Investigator's awareness of the SAE. In addition, all SAEs must be recorded on the AE case report form (CRF) in real time.

All additional follow-up evaluations of the SAE must be reported to BioCryst or its designee as soon as they are available.

The SAE report forms should be sent to the following email addresses or fax numbers:

Email: [[contact]](mailto:[contact]) **and** [[contact]](mailto:[contact])

OR

[contact] **and** [contact]

Immediate reporting should allow BioCryst to take the appropriate measures to address potential new risks in a clinical trial. Therefore, the initial report should be submitted by the Investigator within a very short period of time and under no circumstances should this period exceed 24 hours following awareness of the SAE.

The follow-up report should allow BioCryst to determine whether the SAE requires a reassessment of the benefit-risk profile of the study drug in clinical trial, if the relevant information was not already available and provided in the initial report.

Any SAEs considered possibly, probably or definitely related to treatment and not in accordance with information in the Investigator's Brochure will be reported to the FDA and other Regulatory Competent

Authorities as applicable via the MedWatch/CIOMS reporting system in accordance with FDA and other applicable regulations.

The Principal Investigator or designee at each site is responsible for submitting the Investigational New Drug (IND) safety report (initial and follow-up) or other safety information (e.g., revised Investigator's Brochure) to the Institutional Review Board (IRB) and for retaining a copy in their files.

#### **11.1.6. Pregnancy**

Any pregnancy in an enrolled subject or discovered in a subject during the course of the trial must be reported to BioCryst or designee on the Pregnancy Notification Form (to be supplied by BioCryst) in the same manner as SAEs (see Section 11.1.5). All pregnancies will be followed to an outcome (i.e., miscarriage, elective termination, stillbirth, live birth), and the outcome needs to be reported on the Pregnancy Outcome Form (to be supplied by BioCryst). Pregnancy outcomes of miscarriage, elective termination, stillbirth or birth defects will be considered SAEs and should be reported as per Section 11.1.5.

#### **11.1.7. Reporting DAIDS Grade 3 or 4 events**

Any DAIDS Grade 3 and Grade 4 clinical AE or laboratory abnormality that is judged to be possibly, probably, or definitely related to study treatment but does not meet seriousness criteria will be promptly (within 72 hours) reported to the study medical monitor via telephone or email.

### **11.2. Clinical Laboratory Evaluations**

#### **11.2.1. Clinical Chemistry Profiles**

Clinical chemistry profiles will include a Chemistry 20 panel (includes sodium, potassium, chloride, total CO2 [bicarbonate], creatinine, glucose, urea nitrogen, albumin, total calcium, total magnesium, phosphorus, alkaline phosphatase, alanine aminotransferase (ALT), aspartate aminotransferase (AST), total bilirubin, direct bilirubin, lactate dehydrogenase (LDH), total protein, total creatine kinase, and uric acid).

Blood samples for clinical chemistry profiles will be collected at Screening and at Day 7 or early termination visit (if the early termination visit occurs prior to Day 7). Clinically significant results should be reported as AEs. If Day 7 clinical chemistry profiles are, in the opinion of the investigator, significantly abnormal or significantly changed from baseline at Day 7, they should be repeated at the Day 14 visit.

At screening, creatinine clearance will be calculated by the Cockcroft-Gault equation (using actual body weight and serum creatinine) (see Appendix 16.1).

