**Table 1. BCX1812-306: Schedule of Assessments**

Assessments	Screening 	Baseline  (Pre-dose)	Day 1 Treatment Day 	Day 3	Day 7 (+ 2 days)	Day 14 (+ 3 days) / End of Study	Early Withdrawal
Informed Consent	X						
Inclusion/Exclusion Criteria	X						
Medical History/Physical Exam	X			X 	X 		
Vital Signs 	X			X	X	X	X
Body Temperature 	X	X	X	X	X	X	X
Clinical Chemistries and Hematology 		X			X		X
Urinalysis 		X			X		X
Pregnancy Test (Urine or Serum)	X					X	X
Assessment of influenza symptoms 	X		X	X	X	X	X
Ability to Perform Usual Daily Activities 		X		X	X	X	X
Influenza Related Complications (IRC) 	X			X 	X	X	X
Concomitant Medications Review	X		X	X	X	X	X
Subject Diary Review			X	X	X	X	X
Pharmacokinetic (PK) Sampling			X				
Serum sample for influenza antibody analysis 		X		X	X		X
Swabs for Virology Analysis		X		X	X		X
Rapid antigen test (RAT) or FDA- approved PCR test for influenza A and B on nasal specimen	X						

Assessments	Screening	Baseline (Pre-dose)	Day 1 Treatment Day	Day 3	Day 7 (+ 2 days)	Day 14 (+ 3 days) / End of Study	Early Withdrawal
Study Drug Administration			X				
Adverse Events 	X	X	X	X	X	X	X

- 1 It is expected that the date of Screening, Baseline, and Day 1 (date of study drug administration) will be the same. Day 1 consists of pre and post-dose assessments.
- 2 Vital sign measures will include blood pressure, pulse rate, and respiration rate. Vital signs will be recorded once during Screening, and vital signs will be taken once on remaining study visit days.
- 3 The investigator will record oral body temperature at Screening. Thereafter, the subject or care giver will record oral body temperature approximately every 12 hours in the Subject Diary until temperature normalizes for 48 hours (i.e. temperature without antipyretic is < 37.4°C/ 99.4°F orally for 4 measurements).
- 4 Clinical laboratory assessments performed at Screening are for the purpose of establishing a baseline. Subjects may be enrolled and begin treatment with study drug prior to receiving results. These labs may be done at any visit if necessary for patient management or adverse event monitoring purposes.

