#### **11.2.2. Hematology Profiles**

Hematology profiles will include complete blood count (CBC) with differential. Blood samples for hematology profiles will be collected at Baseline and at Day 7 or early termination visit (if the early termination visit occurs prior to Day 7). If Day 7 hematology profiles are, in the opinion of the investigator, significantly abnormal or significantly changed at Day 7, repeat at the Day 14 visit.

Clinically significant results should be reported as AEs.

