### **11.2.3. Urinalysis**

Urinalysis will include tests for protein, glucose, ketones, blood, urobilinogen, nitrite, pH, and specific gravity and microscopic evaluation (if initial assessment is abnormal) for red blood cells (RBCs) and white blood cells (WBCs).

Urine samples for urinalysis will be collected at Screening, Day 7 and/or at early termination visit (if the early termination visit occurs prior to Day 7). If a urinalysis result for any analyte is, in the opinion of the investigator, significantly abnormal and/or unexplained, repeat testing may be obtained at periodic intervals as deemed appropriate by the Investigator, and should be repeated during the Day 14 visit.

Clinically significant results should be reported as AEs.

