Any event reported on the CRF that occurs on or after the initiation of study drug and not more than 14 days after the last dose of study medication is considered treatment-emergent.

Additionally, it is assumed that an AE which was reported to have started on Day 1 without an associated onset time may have occurred after the initiation of study drug. Hence, AEs occurring on Day 1 with no associated onset time are assumed to be treatment-emergent.

Treatment-emergent Laboratory Abnormalities

A treatment-emergent laboratory abnormality is defined as an increase of at least one toxicity grade from the baseline assessment at any post baseline visit up to and including 14 days after the last dose date of study drug. If no assessment is available at baseline, the screening assessment will be used to assign the baseline toxicity grade. If the relevant baseline and screening assessments are missing, then any graded abnormality (ie, at least Grade 1) is considered to be treatment-emergent.

Concomitant Medications

Concomitant medications are those medications taken upon or after the initiation of study drug.

Prior Medications

Prior medications are those medications taken prior to the initiation of study drug. Subjects will record all medications they are currently taking.

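### A clinically significant pre-dose laboratory result reported as an AE without an onset time can be counted as treatment-emergent

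*Protocol*

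**What the plan says.** **Which results become AEs.** Protocol 11.2.1 sets the chemistry samples: "Blood samples for clinical chemistry profiles will be collected at Screening and at Day 7 or early termination visit". It then states: "Clinically significant results should be reported as AEs". Protocol 11.2.2 and 11.2.3 repeat that instruction for hematology ("Blood samples for hematology profiles will be collected at Baseline and at Day 7") and urinalysis ("Urine samples for urinalysis will be collected at Screening, Day 7 and/or at early termination visit"). None of the three sections limits it to post-dose results or to worsening from baseline.

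**When AEs are collected.** Protocol 11.1.2: "Reports of AEs are to be collected from the time the subject signs the informed consent". Table 1 also marks AE collection at Screening and Baseline.

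**Dates.** Table 1, footnote 1: "It is expected that the date of Screening, Baseline, and Day 1 (date of study drug administration) will be the same". Footnote 4 describes the pre-dose laboratory tests as a baseline and adds: "Subjects may be enrolled and begin treatment with study drug prior to receiving results".

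**How the SAP classifies them.** SAP 3.3.8: "AEs occurring on Day 1 with no associated onset time are assumed to be treatment-emergent". Its stated reason is that such an event might have begun after dosing. SAP 3.3.5 also moves an incomplete non-diary date to Day 1 when its month and year match those of Day 1. SAP 5.3.1 lists AEs that began before treatment but keeps them out of the tables.

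**The concern.** The missing-time rule suits an event whose timing is unknown. A finding from a pre-dose specimen is different, because the draw fixes it before the infusion. No rule in the SAP links a laboratory AE to its specimen, so such a finding dated Day 1 without a time is treated like any other event of unknown timing.

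Safety is the primary endpoint (Protocol 7.1.1), and the study has one arm. A pre-existing abnormality counted as emergent would therefore be read against peramivir with no concurrent control rate beside it. The entry criteria in Protocol 8.1 include histories of renal impairment, liver disease, diabetes and blood dyscrasias, and known neutropenia, so abnormal pre-dose values are foreseeable. If relationship to study drug is also missing, SAP 5.3.1 assigns the strongest category.

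**Working it through.** The plan states no figure on this point: there is no hypothesis test and no sample size calculation. The check is textual, followed by an illustration.

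**Textual chain.** A pre-dose finding reaches the TEAE tables only if all of these hold:

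1. The investigator judges the pre-dose result clinically significant and reports it as an AE. Protocol 11.2.1 to 11.2.3 permit this, and AE collection is already open.
2. The AE is dated Day 1. This is the expected case with same-day screening and dosing, and SAP 3.3.5 can also produce it for an incomplete date.
3. No onset time is recorded. SAP 3.3.8 then makes it treatment-emergent. With a pre-dose time, SAP 5.3.1 removes it from the tables.

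**Weight of one subject.** One misclassified subject adds 100/N percentage points to the rate for its term, provided the subject has no genuine event under that term:

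- N = 120 (planned total): 100/120 = 0.83
- N = 80 (minimum elderly): 100/80 = 1.25
- N = 40 (120 − 80, under 65 years if exactly 80 are elderly): 100/40 = 2.5

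**Illustration.** Let q be the share of subjects with a pre-dose result reported as a Day 1 AE, and m the share of those records with no onset time. The documents give neither, so both are assumptions. Expected false TEAE subjects = N × q × m. If every false case fell on one term with true rate p, and independently of genuine events, the observed rate would be 1 − (1 − p)(1 − qm). Take p = 5.3%, the hyperglycemia rate at 600 mg in Protocol 5.3.1.2. The last column is the binomial probability of at least 12 of 120 subjects, the threshold for the SAP's table of TEAEs in at least 10% of subjects.

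| q | m | False cases, N = 120 | Observed rate if p = 5.3% | P(at least 12 of 120) |
|---|---|---|---|---|
| any | 0 | 0 | 5.3% | 0.026 |
| 2% | 10% | 0.24 | 5.5% | not computed |
| 5% | 50% | 3.0 | 7.7% | 0.21 |
| 10% | 50% | 6.0 | 10.0% | 0.55 |
| 10% | 100% | 12.0 | 14.8% | 0.95 |

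For example, q = 5% and m = 50% give qm = 0.025, so 120 × 0.025 = 3.0 cases and 1 − 0.947 × 0.975 = 7.7%. Putting every false case on one term is the extreme; spread over several terms, each would move less.

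**After the fix.** If every pre-dose laboratory finding is recognised as such, qm = 0, the rate stays at 5.3% and the probability stays at 0.026.

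**The case against.** The strongest reply is that the AE definition already settles the matter. Protocol 11.1.1.1 describes an AE in terms of something that develops or gets worse during the study, and Table 1 footnote 4 treats the pre-dose tests as a baseline. On that reading a stable abnormality is baseline data or medical history. Much of this stands: many investigators will not report such findings, least of all those expected from a known condition. It does not close the route. The definition is permissive, and the same section classes clinically relevant abnormal laboratory findings as AEs without requiring a change from baseline. It sends conditions to medical history only in the context of planned surgery.

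It can also be said that counting events of unknown timing is a conservative safety convention, and that subject-level listings would let a reader compare a Day 1 laboratory AE with its baseline value. Both are fair. But here the timing can be established, and a listing does not correct a table.

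A practical reply is that specimen times may be missing. Protocol 10.1.2.2 asks for clock times for the pharmacokinetic samples, whereas 10.1.2.1 sets no such requirement for the safety laboratory draw. This stands for the time alone. The nominal visit, which SAP 3.3.6 already uses, still separates the pre-dose sample from Day 7.

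Three stronger readings are tempting:

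- **Reporting is mandatory and inflation certain.** The protocol says should, and SAP 5.3.1 removes AEs with a recorded pre-dose time.
- **The time the result arrives would be entered as onset, making the event post-dose.** Results may indeed arrive after dosing, but nothing tells sites to use that time.
- **The graded laboratory tables are distorted too, or must agree with the AE tables.** SAP 3.3.8 requires a rise of at least one grade from baseline, falling back to Screening. Only if both values are missing does any graded abnormality count. The two sets of tables use different definitions and need not match.

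**Conclusion.** The gap is real and conditional. Pre-dose laboratory findings can enter the TEAE tables when they are reported as AEs dated Day 1 with no onset time. For those records the SAP's justification cannot hold. AEs with a recorded pre-dose time are handled correctly, and the graded laboratory tables are normally protected.

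The supported size is per subject: 0.83 percentage points at N = 120, 1.25 at N = 80 and 2.5 at N = 40 for the affected term. The any-TEAE rate moves only if the subject has no other TEAE. The total excess starts at zero and has no documented upper value. A reader might infer a sizeable excess from the entry criteria: with 5% to 15% of subjects affected and 50% to 100% of times missing, 3 to 18 of 120 would be misclassified. Those inputs are not in the documents, and that range leaves out zero, which the text allows. The change is worth making because it is cheap and concerns the primary safety tables.

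**What to change.** **SAP 3.3.8.** State that an AE reporting a laboratory result takes its onset from the specimen collection date and time or, if the time is missing, from the nominal visit. A finding from the Screening/Baseline (pre-dose) specimen is then listed but not counted as treatment-emergent unless it worsens after dosing. Apply the Day 1 missing-time assumption to these AEs only when neither specimen time nor nominal visit is available.

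**Protocol 11.2.1 to 11.2.3.** Limit laboratory AEs to post-dose results that are new or worse than baseline, and record clinically significant pre-dose findings as medical history. This brings the three sections into line with 11.1.1.1 and Table 1 footnote 4.

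**Cost.** A short addition to the SAP, one sentence in each of three protocol sections, and some matching of AE records to laboratory records. Infusion start is already recorded (Protocol 9.3). Matching will not be fully automatic: Protocol 11.1.2 asks for a diagnosis in place of individual signs where possible, so an AE recorded as a diagnosis needs manual review. If sites have already finished reporting, the SAP change can still be applied to the data collected, as far as records can be matched.

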#### **11.2.2. Hematology Profiles**

Hematology profiles will include complete blood count (CBC) with differential. Blood samples for hematology profiles will be collected at Baseline and at Day 7 or early termination visit (if the early termination visit occurs prior to Day 7). If Day 7 hematology profiles are, in the opinion of the investigator, significantly abnormal or significantly changed at Day 7, repeat at the Day 14 visit.

Clinically significant results should be reported as AEs.

### **11.2.3. Urinalysis**

Urinalysis will include tests for protein, glucose, ketones, blood, urobilinogen, nitrite, pH, and specific gravity and microscopic evaluation (if initial assessment is abnormal) for red blood cells (RBCs) and white blood cells (WBCs).

Urine samples for urinalysis will be collected at Screening, Day 7 and/or at early termination visit (if the early termination visit occurs prior to Day 7). If a urinalysis result for any analyte is, in the opinion of the investigator, significantly abnormal and/or unexplained, repeat testing may be obtained at periodic intervals as deemed appropriate by the Investigator, and should be repeated during the Day 14 visit.

Clinically significant results should be reported as AEs.

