#### **5.3.1.2. Peramivir Safety**

Safety of various doses of peramivir in acute uncomplicated influenza has been evaluated in 1453 adults. The most frequently observed treatment emergent AEs (TEAEs) across all adult subjects with acute uncomplicated influenza treated with various doses of peramivir were diarrhea (7.4%), decreased neutrophil count (5.5%), and increased blood glucose (5.0%). The only events reported in  $\geq 2\%$  of subjects treated with peramivir 600 mg and for which the rate was greater than placebo were diarrhea (7.6% vs. placebo 7.0%), decreased neutrophil count (5.7% vs. placebo 0.0%), hyperglycemia (5.3% vs. placebo 4.8%) and urine leukocytes (2.8% vs. placebo 1.8%). Adverse event (AE) rates overall were similar to placebo and oseltamivir. No safety signals have emerged from these trials.

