## **7. INVESTIGATIONAL PLAN**

### **7.1. Endpoints**

#### **7.1.1. Primary Endpoint**

The primary endpoint of this study will be safety and include the assessment of AEs, laboratory abnormalities (clinical chemistry, hematology and urinalysis), vital signs and physical examinations.

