PARAMETER	GRADE 1 MILD	GRADE 2 MODERATE	GRADE 3 SEVERE	GRADE 4 POTENTIALLY LIFE-THREATENING
Uric acid	7.5 – 10.0 mg/dL 0.45 – 0.59 mmol/L	10.1 – 12.0 mg/dL 0.60 – 0.71 mmol/L	12.1 – 15.0 mg/dL 0.72 – 0.89 mmol/L	> 15.0 mg/dL > 0.89 mmol/L
URINALYSIS Standard International Units are listed in italics				
Hematuria (microscopic)	6 – 10 RBC/HPF	> 10 RBC/HPF	Gross, with or without clots OR with RBC casts	Transfusion indicated
Proteinuria, random collection	1 +	2 – 3 +	4 +	NA
Proteinuria, 24 hour collection				
Adult and Pediatric ≥ 10 years	200 – 999 mg/24 h 0.200 – 0.999 g/d	1,000 – 1,999 mg/24 h 1.000 – 1.999 g/d	2,000 – 3,500 mg/24 h 2.000 – 3.500 g/d	> 3,500 mg/24 h > 3.500 g/d
Pediatric > 3 mo - < 10 years	201 – 499 mg/m  /24 h 0.201 – 0.499 g/d	500 – 799 mg/m  /24 h 0.500 – 0.799 g/d	800 – 1,000 mg/m  /24 h 0.800 – 1.000 g/d	> 1,000 mg/ m  /24 h > 1.000 g/d

\* Values are for term infants. [Preterm infants should be assessed using local normal ranges.](#)

† Use age and sex appropriate values (e.g., bilirubin).

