Table 14.3.4.1.1	Summary of Chemistry Laboratory Values by Study Visit: Safety Population
Table 14.3.4.1.2	Summary of Hematology Laboratory Values by Study Visit: Safety Population
Table 14.3.4.2	Graded Laboratory Toxicities: Safety Population
Table 14.3.4.3.1	Laboratory Shifts from Baseline to Day 7 - Chemistry: Safety Population
Table 14.3.4.3.2	Laboratory Shifts from Baseline to Day 7 - Hematology: Safety Population
Table 14.3.4.3.3	Laboratory Shifts from Baseline to Day 7 - Urinalysis: Safety Population
Table 14.3.5	Study Drug Exposure: Safety Population
Table 14.3.6	Summary of Vital Signs by Study Visit: Safety Population
Table 14.3.7.1	Concomitant Medications by Generic Name and Drug Classification: Safety Population
Table 14.3.7.2	Antipyretic Concomitant Medications by Generic Name and Drug Classification: Safety Population
Table 14.3.7.3	Concomitant Medications Used to Treat Influenza Symptoms by Generic Name and Drug Classification: Safety Population
Table 14.4.1.1	Summary of Plasma Concentrations of Peramivir by Time Point: Intent-to-Treat Population
Table 14.4.1.2	Summary of Plasma Concentrations of Peramivir by Time Point: Exposure-Response Population
Figure 14.4.2	Relationship between Time to Alleviation of Influenza Symptoms and Peramivir Plasma Concentrations at 30-60 Minutes Post-Dose: Exposure-Response Population

Output Number	Output Title
Figure 14.4.3	Relationship between Viral Change from Baseline and Peramivir Plasma Concentrations at 30-60 Minutes Post-Dose: Exposure-Response Population
Listing 16.2.1	Study Completion: Intent-to-Treat Population
Listing 16.2.2	Protocol Deviations: Intent-to-Treat Population
Listing 16.2.4.1	Inclusion/Exclusion Criteria: Intent-to-Treat Population
Listing 16.2.4.2	Subject Eligibility: Intent-to-Treat Population
Listing 16.2.4.3	Demographics: Intent-to-Treat Population
Listing 16.2.4.4	Medical History: Intent-to-Treat Population
Listing 16.2.4.5	Prior and Concomitant Medications: Intent-to-Treat Population
Listing 16.2.5.1	Study Medication Administration: Intent-to-Treat Population
Listing 16.2.5.2	Pharmacokinetic Sample Collection Time and Concentrations: PK Population
Listing 16.2.6.1.1	Summary of Efficacy Variables: Intent-to-Treat-Infected Population
Listing 16.2.6.2	Influenza Symptoms: Intent-to-Treat Population
Listing 16.2.6.3	Temperature: Intent-to-Treat Population

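### No required urine test would detect leukocytes when they are the only finding, although the protocol lists urine leukocytes among four events reported above placebo at 600 mg

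*Protocol*

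**What the plan says.** Protocol 11.2.3 defines the panel: "Urinalysis will include tests for protein, glucose, ketones, blood, urobilinogen, nitrite, pH, and specific gravity and microscopic evaluation (if initial assessment is abnormal"). The microscopy is for red and white cells. Samples are taken at Screening (Baseline in Table 1) and Day 7 or early termination, with a repeat at Day 14 if the investigator judges a result significantly abnormal. Clinically significant results are to be reported as adverse events.

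Protocol 5.3.1.2 names the events reported in at least 2% of subjects on 600 mg and more often than on placebo: "diarrhea (7.6% vs. placebo 7.0%), decreased neutrophil count (5.7% vs. placebo 0.0%), hyperglycemia (5.3% vs. placebo 4.8%) and urine leukocytes (2.8% vs. placebo 1.8"%).

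Protocol 7.1.1 makes safety the primary endpoint, including "laboratory abnormalities (clinical chemistry, hematology and urinalysis), vital signs and physical examinations".

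On the analysis side, SAP 5.3.3 names chemistry and hematology analytes but no urine analytes, and grades laboratory abnormalities by the DAIDS table. SAP section 9 plans by-visit summary tables for chemistry and hematology only. Urinalysis gets one shift table, "Laboratory Shifts from Baseline to Day 7 - Urinalysis: Safety Population" (Table 14.3.4.3.3), and Listing 16.2.8.1.3. The urinalysis part of the DAIDS table in Protocol Appendix 2 has rows for "Hematuria (microscopic") and proteinuria, and none for white cells.

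**The concern.** The protocol singles out urine leukocytes in its own summary of earlier safety experience, then specifies a urine panel that does not test for them directly. White cells come into view only through another abnormal result. A subject with leukocytes and nothing else abnormal passes through both scheduled urinalyses without any required test that could show it.

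This is a safety study, and urinalysis is part of its primary endpoint. If few or no urine leukocyte findings are reported, a reader cannot tell absence of the finding from absence of the test. When microscopy does show white cells, the planned grading has no category in which to summarise them.

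**Working it through.** The plan states no figure on this point and tests no hypothesis (Protocol 13.3), so there is nothing to reproduce. The check is a comparison of sections, followed by a scale calculation.

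**Step 1: how each of the four events is ascertained.** Rates are from Protocol 5.3.1.2; differences are 600 mg minus placebo, in percentage points.

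| Event | 600 mg | Placebo | Difference | Required ascertainment |
|---|---|---|---|---|
| Diarrhea | 7.6% | 7.0% | 0.6 | Adverse event collection in all subjects (11.1.2) |
| Decreased neutrophil count | 5.7% | 0.0% | 5.7 | Blood count with differential, Baseline and Day 7 (11.2.2) |
| Hyperglycemia | 5.3% | 4.8% | 0.5 | Glucose in the chemistry panel, Screening and Day 7 (11.2.1) |
| Urine leukocytes | 2.8% | 1.8% | 1.0 | Microscopy, only after an abnormal initial assessment (11.2.3) |

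Urine leukocytes is the only one of the four whose detection depends on a different result.

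**Step 2: whether another section fills the gap.** The schedules of assessments in both documents say only that urinalysis is done. SAP 5.3.3 lists no urine analytes. No section adds a routine urine leukocyte test.

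**Step 3: direction.** A sample with leukocytes and an abnormal listed test goes to microscopy. A sample with leukocytes alone need not. Relative to testing every sample, the number of subjects found with the finding can be too low but not too high.

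**Step 4: scale.** Inputs: N = 120 planned, at least 80 of them elderly (Protocol 10.1); rates of 2.8% and 1.8%. Expected count = N × p; chance of at least one case = 1 − (1 − p)^N. Both assume that every sample is tested and that the earlier rate applies.

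- N = 120, p = 0.028: 120 × 0.028 = 3.36; 1 − 0.972^120 = 0.967
- N = 120, p = 0.018: 120 × 0.018 = 2.16; 1 − 0.982^120 = 0.887
- N = 80, p = 0.028: 80 × 0.028 = 2.24; 1 − 0.972^80 = 0.897
- N = 80, p = 0.018: 80 × 0.018 = 1.44; 1 − 0.982^80 = 0.766

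The documents do not give the share of cases in which leukocytes are the only finding, so the number missed cannot be computed from them.

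**The case against.** The strongest objection is that little would change even with perfect detection. The study is single-arm and descriptive. Three cases in 120 give an exact 95% interval of about 0.5% to 7.1%, which covers both the 2.8% and the 1.8%. Section 5.3.1.2 also says that overall adverse event rates were similar to placebo and oseltamivir and that no safety signal emerged. This stands, and it limits the weight of the point. It does not explain why one of the four listed events should be ascertained conditionally.

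The second objection is that the panel is a minimum. The wording of 11.2.3 does not bar a strip that also reads leukocytes, and footnote 4 to Table 1 allows laboratory tests at any visit for patient management or adverse event monitoring. A symptomatic urinary event would be an adverse event whatever the strip shows. This also stands, so a reader who infers that isolated leukocytes would never be detected goes too far. What is missing is a required test, and optional local testing would make detection uneven rather than complete.

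The third objection concerns reporting. All data are listed, and clinically significant results reach the adverse event tables, so findings that are made are not lost. That is correct; what they lack is a defined summary category.

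Three further inferences are tempting but not supported:

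- *The study's rate could not be compared with the earlier 2.8%.* The documents do not say how the earlier trials ascertained urine leukocytes. If they used a similar conditional panel, 2.8% already reflects it, and discounting it for isolated cases would count the loss twice. It is also an adverse event rate, not a rate of positive tests.
- *The panel would leave few or no events.* Suppose 2.8% is a full-detection rate and assume that 25%, 50% or 75% of cases are isolated. The chance of detecting at least one in 120 is then 1 − (1 − 0.028 × 0.75)^120 = 0.92, 1 − (1 − 0.028 × 0.50)^120 = 0.82 or 1 − (1 − 0.028 × 0.25)^120 = 0.57. Those shares are arbitrary, and a low count is expected anyway.
- *Detection is worse in diabetic or elderly subjects.* Glucose and protein are on the panel, and an abnormal result on either leads to microscopy. The documents do not show poorer detection in these groups.

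**Conclusion.** The point holds in a limited form. Protocol 11.2.3 requires no test that would find urine leukocytes when they are the only abnormality. They are one of four events that the protocol itself reports in at least 2% of 600 mg subjects and above placebo, and the only one of the four not ascertained in every subject. The resulting count can only be understated, by an unknown share.

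The size is modest. At 2.8%, about 3 cases in 120 would be expected with full detection, and the earlier excess over placebo was 1.0 percentage point. The conclusion rests on reading the initial assessment in 11.2.3 as the eight listed tests and on sites doing no more than the protocol requires. It does not depend on how the 2.8% was obtained; only the expected count does. This is an inexpensive improvement to a primary safety measure, not a flaw that threatens the study's conclusions.

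**What to change.** In Protocol 11.2.3, add leukocyte esterase to the dipstick list and count a positive result as an abnormal initial assessment that leads to microscopy, at Baseline, Day 7 and any repeat.

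In SAP 5.3.3, name the urine analytes. In Table 14.3.4.3.3, add a categorical (negative/positive) Baseline-to-Day 7 shift for urine leukocytes, since the DAIDS urinalysis rows cover only hematuria and proteinuria. Show the number of subjects tested at each visit. If samples have already been collected under the present panel, the SAP change is still useful: it keeps untested from being read as negative.

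The cost is one more analyte on urine already collected and one row in a planned table. The downside is a few more microscopies and some incidental positives, for example from urinary infection.
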